NAS is manifested by central nervous system irritability (high pitch and inconsolable crying, irritability and sleep disturbances), autonomic nervous system over-reactivity (sweating, yawning, sneezing), gastrointestinal manifestations (poor feeding, emesis and loose stools) and respiratory distress (tachypnea and nasal congestion) (Finnegan 1975; Finnegan, 1976; Kaltenbach, 1986; Desmond 1975). The standard of care is to treat these infants with a slow taper of opioid but to date there is no established gold standard for that taper (Cochrane, 2010). The lack of high-quality research in the treatment of NAS has led to wide variations in medications and protocols (Patrick, 2014; O'Grady, 2009; Sarkar, 2006) and data on changes in the utilization of NICU resources in the treatment of affected infants are lacking (Tolia, 2015).

For the time frame July 1, 2013 through September 30, 2014, 300 infants with NAS have been cared for at the Johns Hopkins All Children's Hospital (JHACH) NICU with an average length of stay of 30 days. The average length of stay has recently decreased to 22-25 days with implementation of strict management guidelines and protocols. Accounting for an average daily cost of \$2062.50, the burden translates into medical costs averaging \$48,468.75 per infant. With the proposed model involving methadone treatment, we anticipate at most 14 days of care in the NICU at a cost of \$28,875.00, followed by 10 days of home care at an anticipated cost of \$190/day for a total cost of \$30,775. This is an anticipated reduction in cost of \$17,693.75 per patient.

The prolonged stay has other social and medical impacts – including limitation in parental interaction and bonding, exposure to nosocomial infections, and taking up valuable resources both in terms of personnel and equipment. Once discharged home, these infants are often exposed to inconsistent caregiving, family instability, out of home placements, chronic stress, abuse, neglect and poverty – all of which affect their health and development, thus incurring even greater societal costs. To date, there are no published data on the in-home pharmacologic treatment of these infants.

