It is standard of care for infants discharged from the JHACH NICU to see their primary care provider (PCP) within a day or two of discharge. Follow-up will be provided by an IRB approved study team JHACH Pediatrician, and will take place within one or two days after discharge then weekly for 4 weeks after discontinuation of methadone treatment.

G. Off-treatment Criteria:

Principal Investigator: [name], MPH

Application Number: IRB00107690

Off-treatment is defined as an infant who no longer qualifies for discharge home on methadone – i.e. requiring adjuvant pharmacological therapy or re-admission to the hospital while still on methadone

1. Addition of adjuvant therapy:

It is common for infants suffering from NAS to require the addition of an adjunct therapeutic agent for control of symptoms. This second-line agent varies among institutions but consists often of phenobarbital.

If demonstration project participants have uncontrolled NAS symptoms (defined as a 24-hour Finnegan score average ≥ 11 despite comfort measures and maximal methadone dosing – i.e. 0.1 mg/kg given every 4 hours), the infant will be placed on phenobarbital, the standard of care at JHACH NICU. Such infant will be off-treatment from the study i.e. will not qualify for subsequent discharge home prior to discontinuation of methadone. Maternal assessments of bonding and depression will remain ongoing. There will be no home nursing visits.

2. Re-admission to the JHACH NICU:

It is common for infants suffering from NAS not to tolerate weaning off medication. Re-escalation during that phase is common. If during the weaning phase, infant's Finnegan scores are > 8 on 2 consecutive scores despite comfort measures, the dose of methadone will be increased to the previous dose at which the patient's symptoms were well controlled.

If an infant requires consecutive re-escalation of medication with no control of symptoms (i.e. 24 hour Finnegan scores > 6), such infant will be re-admitted to the hospital.

- for infants who were discharged home on a dose of methadone that is < 0.04 mg/kg, such infant will be re-admitted to the hospital if consecutive re-escalation of methadone are required and infant reaches a dose of 0.05 mg/kg.

- for infants discharged home at a dose of 0.04 mg/kg, who do not tolerate weaning at home and who require dose escalation, the dose will be increased in 2 increments per protocol to a value of 0.07 mg/kg before re-admission to the hospital.

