JHACH admitted and average of 131 NAS infants in recent years who required pharmacological treatment for NAS. Approximately 30% of those mother/infant dyads were residents of PAR. We anticipate to enroll 25 mother/baby dyads into the methadone treatment group and 25 mother/baby dyads into the control group for a total of 100 participants. Both the mother and infant are research participants. Those infant participants are defined as 1) needing methadone or other opiate treatment, 2) transitioning to home care, and 3) successfully weaning off medication.

This number has been extrapolated taken into account the following projections/assumptions: 1) not all mothers staying at PAR will meet criteria for participation, and 2) polydrug use may be discovered at the time of delivery thus excluding from participation, and 3) 20-40% of infants enrolled may need adjunct second line therapy.

b. Blinding, including justification for blinding or not blinding the trial, if applicable.

This is a demonstration study with no blinding of subjects involved.

c. Justification of why participants will not receive routine care or will have current therapy stopped.

All infants will continue to receive routine hospital care. Methadone treatment is approved by the FDA, and endorsed by the AAP for inpatient and outpatient treatment of infants with NAS. While methadone is not used as the standard of care at JHACH NICU for infants with NAS at birth, it is still used for later iatrogenic withdrawal in the NICU and other intensive care units in the hospital.

d. Justification for inclusion of a placebo or non-treatment group. N/A Will need to justify this as a comparison groups has been included

e. Definition of treatment failure or participant removal criteria.

As delineated above, infants will be off-treatment from the demonstration project if 1) they require the addition of a second-line of pharmacological treatment or 2) they require re-admission to the

Principal Investigator: [name], MPH

Application Number: IRB00107690

hospital. Data will still be collected until final hospital discharge for these infants and the maternal assessments of bonding and depression will remain ongoing. .

Other Indications for participant off-study:

- a. Parent withdraws informed consent at any time
 - b. Infant transfers to another hospital.
 - c. Infant experiences an unexpected adverse event deemed related to study intervention

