- a. **Primary outcome variable:** Length of Stay (LOS)

- b. **Additional outcomes of interest to be examined:**

- 1) Maternal bonding measured by the Postpartum Bonding Questionnaire (PBQ);
- 2) Depressive symptomatology measured by Edinburgh Postnatal Depression Scale (EPDS);
- 3) Hospital readmission within 30 days;
- 4) Weight gain of greater than 15% above Birth Weight at 30 days of age;
- 5) Age appropriate development as screened by the Ages and Stages questionnaires.

- c. **Statistical plan including sample size justification and interim data analysis:**

Demographic and clinical characteristics of participants will be summarized using means with standard deviations (SD) or median with interquartile ranges for continuous variables and counts and percentages for categorical variables. The primary outcome, length of stay, will be summarized using mean (SD) or median and interquartile range and will be compared to the comparison group using the t-test or Wilcoxon rank sum test as appropriate. For the secondary outcomes, the scores on the postpartum bonding questionnaire or the Edinburgh Postnatal Depression Scale will be summarized using means (SD) and compared to other patients in the comparison group using independent two-sample t-test. The proportion of participants that are readmitted within 30 days or with a weight gain of greater than 15% above birth weight will be compared to the comparison group using a Chi-squared or Fishers exact test as appropriate. Among the methadone cohort, we will calculate percentage of infants with age appropriate development at 4, 8 and 12 months. We anticipate that 25 mother-child dyads in each group will be available for the study. We expect that the mean LOS in the comparison group will be around 25 days (based on historical data). This sample size will allow us to estimate differences in LOS of >4 days with sufficient power (80%) at an alpha of 0.05, assuming a standard deviation of 5 days for both groups.

Early stopping rules:

Infant: requiring therapy with a second drug

Parents: desire to remove the infant from the study at any time or when infant is transferred to another hospital.

7. Risks

- a. **Medical risks, listing all procedures, their major and minor risks and expected frequency:**

Principal Investigator: [name], MPH

Application Number: IRB00107690

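### The 80% power for a 4-day difference in length of stay leaves out the protocol's own forecast that 20-40% of treated infants may lose early discharge, and section 6.c does not say whether those infants are analysed

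*Combined protocol and SAP*

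**What the plan says.** Section 6.c (Statistical plan) expects 25 dyads per group and a mean LOS of about 25 days in the comparison group. It then states: "This sample size will allow us to estimate differences in LOS of >4 days with sufficient power (80%) at an alpha of 0.05". The spread behind this figure is set by "assuming a standard deviation of 5 days for both groups", and no source is given for that value. The primary test is left open between the t-test and the Wilcoxon rank sum test.

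Four other places bear on that sentence.

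- Background (section 3), cost model: "we anticipate at most 14 days of care in the NICU", followed by 10 days of home care.
- Accrual: "20-40% of infants enrolled may need adjunct second line therapy".
- Off-treatment Criteria, item 1: an infant given adjuvant therapy "will not qualify for subsequent discharge home prior to discontinuation of methadone".
- Item e (treatment failure or participant removal): data on off-treatment infants are still collected to final hospital discharge.

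The Accrual section also describes infant participants as those who need opiate treatment, move to home care and wean successfully, and says the enrolment number took the adjunct forecast into account. Section 6.c does not say which infants enter the primary comparison.

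**The concern.** Early discharge on methadone is the route by which LOS is meant to fall, and the protocol expects a fifth to two-fifths of infants to lose it. If they are analysed, the methadone group is a mixture of short and long stays. The mixture has two effects: the methadone SD rises above the SD within each part, and the group's mean difference is smaller than the benefit in infants sent home early. Section 6.c carries neither effect into its power statement.

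If they are not analysed, the problem is different. The methadone group would be selected on treatment success and would lose its longest stays, with no matching selection in the comparison group. The plan can be read either way, so the reader cannot tell which comparison the 80% describes.

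**Working it through.** **Inputs from the documents.** n = 25 per group; alpha 0.05 (sidedness not stated, two-sided assumed because one-sided gives 87-88%); difference 4 days; SD 5 in each group; comparison mean 25 days; share f needing adjunct therapy 0.2 to 0.4; at most 14 NICU days then 10 home days.

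**Assumptions, not in the documents.** Mean stay of off-treatment infants: 24 days (14 + 10, all in hospital) or 25 days (the comparison mean). SD within each part of the mixture: w = 5, with w = 4 as a sensitivity value.

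**1. The plan's own figure.** SE = √((5² + 5²)/25) = 1.414, and 4/1.414 = 2.83 on 48 df. Noncentral t power is 79.1% (80.7% by normal approximation), and the detectable difference at 80% is 4.04 days. The statement reproduces.

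**2. Mixture formulas.** Let h be the mean stay of infants discharged home on methadone, o that of off-treatment infants, and g = o − h.

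- Methadone mean = (1 − f)h + f·o
- Methadone variance = w² + f(1 − f)g²
- Power: Welch noncentral t, with SD 5 in the comparison group

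**3. Overall difference of exactly 4 days (methadone mean 21), w = 5.** Example with o = 25 and f = 0.4: h = (21 − 0.4 × 25)/0.6 = 18.33, so g = 6.67. Variance = 25 + 0.24 × 6.67² = 35.67, so SD = 5.97. SE = √((25 + 35.67)/25) = 1.558, and 4/1.558 = 2.57, giving power 71.0%.

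| o (days) | f | h | g | Methadone SD | Power at 4 days | Detectable difference |
|---|---|---|---|---|---|---|
| 24 | 0.2 | 20.25 | 3.75 | 5.22 | 77.4% | 4.14 |
| 24 | 0.4 | 19.00 | 5.00 | 5.57 | 74.5% | 4.33 |
| 25 | 0.2 | 20.00 | 5.00 | 5.39 | 76.0% | 4.22 |
| 25 | 0.4 | 18.33 | 6.67 | 5.97 | 71.0% | 4.58 |

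The detectable difference is solved with o held fixed, so that g and the SD change with the difference.

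**4. Same scenarios with w = 4.** Power at 4 days runs from 84.6% (o = 24, f = 0.2) to 77.8% (o = 25, f = 0.4).

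**5. If 4 days is the benefit only in infants discharged home on methadone** (o = 25, g = 4, w = 5). The overall difference is 4 × 0.8 = 3.2 days at f = 0.2 and 4 × 0.6 = 2.4 days at f = 0.4. The SDs are 5.25 and 5.37, and power is 58% and 36%.

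**6. Stays implied by the protocol's cost figures** (h = 14, o = 24, comparison 25, w = 5). The methadone mean is 0.8 × 14 + 0.2 × 24 = 16 at f = 0.2 and 0.6 × 14 + 0.4 × 24 = 18 at f = 0.4. The differences are 9 and 7 days, the SDs 6.40 and 7.00, and power 99.97% and 97.8%. If off-treatment stays were longer, power would fall: simulated t-test power with h = 14 is 97% to 56% at o = 30, and 83% to 19% at o = 35.

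**7. Effect of dropping off-treatment infants in scenario 6.** The apparent difference would be 25 − 14 = 11 days instead of 9 to 7, so selection alone would add 2 to 4 days.

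**The case against.** Three objections carry weight.

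First, the 25 may already be net of adjunct cases. The Accrual section says the number took the forecast into account, its description of participants requires home transition and weaning, and section 6.c lists need for a second drug under early stopping rules. On that reading there is no mixture. But item e keeps collecting data on these infants to final discharge, which points the other way, and the net reading brings in the selection shown in step 7. The ambiguity stands on either reading.

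Second, the shortfall depends on inputs that the documents do not give. The 24-day stay is put together from a cost projection for home care, and section 6.c gives 5 as the total SD of a group, not the SD within a part of it. Discharge is tied to a set weaning step, so a narrower spread among infants sent home is plausible. At w = 4 most of the shortfall disappears. This stands, and is why only a range can be given.

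Third, this is a non-randomized feasibility study with ample power at the effect it expects. That stands too, and it limits the consequence to wording.

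A reader might also infer that the protocol's own assumptions give only 62-67% power. That figure takes the methadone SD (6.4 to 7.0) from a 10-day gap between the two kinds of stay, yet holds the overall difference at 4 days. Against a comparison mean of 25, stays of 14 and 24 days give a 7- to 9-day difference, not 4. Having both a 10-day gap and a 4-day difference would need home-discharge means of about 17-19 days and off-treatment means of about 27-29 days, which the documents do not state.

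**Conclusion.** The arithmetic in section 6.c is correct for the assumptions it lists. The defect is that those assumptions do not reflect the forecast in the Accrual section, and that the analysis set is not stated.

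With off-treatment infants included, stays of 24-25 days for them and a within-part SD of 5, power at a 4-day overall difference is about 77-71%, against 79.1% as planned. That is a loss of roughly 2 to 8 percentage points. If the 4 days refers only to infants discharged home on methadone, the loss is much larger. With a within-part SD of 4, power lies on both sides of 80%.

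The documents do not support a claim that the trial is underpowered for the effect it expects, and no increase in sample size follows. That conclusion rests on off-treatment stays near 24 days. If they ran to 30 days or more, power at the expected effect could also fall below 80%.

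**What to change.** Change the wording of section 6.c in three places.

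1. **Analysis set.** State that the primary LOS comparison includes every enrolled infant started on pharmacologic treatment for NAS, including off-treatment infants, whose data are already collected to final discharge. Reconcile this with the Accrual description of participants as those who move to home care and wean, and with the early stopping wording in 6.c.
2. **Primary analysis.** Fix it as the difference in mean LOS, by Welch t-test with a 95% CI, since the power statement concerns a mean difference and equal variances are doubtful. Keep the Wilcoxon test as a sensitivity analysis.
3. **Power statement.** Replace the single 80% with a range labelled as assumption-based, taking SD and mean difference from the same scenario. For example: about 71-77% power at a 4-day overall difference (detectable difference about 4.1-4.6 days) with within-part SD 5, about 78-85% with within-part SD 4, and about 98% or more under stays of 14 or 24 days against 25. Give the source of the SD of 5. Do not enter an SD of 6.4-7.0 or a power of 62-67% as the protocol's own figures.

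The cost is an amendment to the text. It needs no extra patients, visits or data. The stated detectable difference may become slightly less favourable.

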The rationale for amending that protocol relates to the reported premature initiation of Phenobarbital as adjunct therapy. Most protocols call for the initiation of adjunct therapy when first line medication fails (i.e. reaching maximal doses or requiring multiple re-escalations of dosing). In Table 1 however, phenobarbital initiation happens instead during the weaning process. Accordingly, a rather large number of infants get started and discharged home on phenobarbital (22.6%).

Our goal is to introduce second-line treatment when truly indicated (i.e. when maximal safe therapy fails) and to minimize discharge home on medication, as this approach, while minimizing the LOS, allows for infants to remain on medication for an indeterminate length of time.

Principal Investigator: [name], MPH

Application Number: IRB00107690

Demonstration Study Methadone Protocol

Initiation:

Initiate protocol for infants with 2 consecutive Finnegan scores > 8. Starting dose is 0.1 mg/kg/dose Q 6 hours (Table 2 - Step 1). As per hospital policy, medications may be given +/- 1 hour from scheduled administration time

Weaning:

Table 2. Initiation and weaning of methadone			
Step	Methadone Dose (mg/kg)	Interval	Minimum Number of Doses
Step 1	0.1	Q6 h	8
Step 2	0.07	Q12 h	2
Step 3	0.05	Q12 h	2
Step 4	0.04	Q12 h	2
Step 5	0.03	Q12 h	2
Step 6	0.02	Q12 h	2
Step 7	0.01	Q12 h	2
Step 8	0.01	Q24 h	1

Initial weaning: wean after 48 hours of stable scores (i.e. 2 consecutive 24 hour Finnegan score averages < 8)
Subsequent weaning: Wean to the next step if the 24 hour Finnegan score average is < 8;
If the 24-hour Finnegan score average is 8-10, do not wean;
If the 24-hour Finnegan score average is ≥ 11, follow escalation below.

Table 2 Escalation:

- Escalation will take place by going back one step in the dosing regimen (i.e. go from Step 5 to Step 4, etc.)
- If infant needs escalation from Step 2 to Step 1, one may consider either going back up the one step to Step 1 or giving an additional methadone dose.
- Weaning will resume after 24 hours of stable scores (i.e. a 24 hour average of <8)
- If infant fails Step 1 above, increase interval of dosing to Q 4 hour (Step 1A in table 3 below)

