- 3) Observe a 48-hour (instead of 24) of stable scores prior to initial weaning and prior to wean after re-escalation if patient falls in table 2.

C. Discharge home:

Infants will be discharged home or to Operation PAR when they are deemed stable by the treating team.

Principal Investigator: [name], MPH

Application Number: IRB00107690

Stability is defined as:

- 1) A maximal dose of methadone of ≤ 0.04 mg/kg at the time of discharge (Step 4 of Table 2), and
- 2) A history of successful weaning of methadone for a least 3 days prior to discharge, and
- 3) No dose re-escalation in the previous 72 hours prior to discharge.

Timing of medication administration may be changed gradually prior to discharge, as allowed by hospital policy, to accommodate outpatient administration by Kids Home Care.

Weaning at home will follow the weaning protocol delineated above. Finnegan scoring will be continued at home. It will be done twice daily by the visiting Kids Home Care RN. Virtual Finnegan scoring assessment will be done as described above every 3 to 4 hours by teleconferencing with the Kids Home Care RN versed in the care of infants with NAS.

D. Discontinuation of methadone:

Methadone will be discontinued when the dose is 0.01 mg/kg/dose every 24 hours and the previous 24-hour average if ≤ 6 .

E. Home observation post discontinuation of methadone:

Observe infant for 72 hours off medication with twice daily nursing visits. Treatment is considered successful if infant's 24-hour average remains < 8 .

This observation period is important as it allows to watch for possible rebound of symptomatology after cessation of medical intervention, and is in accordance with the standard of care that infants with NAS receive at JHACH. If during this observation period infants develop rebound symptomatology (defined as a 24 hour Finnegan score average of > 8), the nurse will institute appropriate measures of comforting infant and reducing / eliminating noxious stimuli. If comfort measures fail and Finnegan scores remain > 8 on 2 consecutive assessments performed at 3-4 hour intervals, methadone will be resumed at the last dose that infant received prior to discontinuation. Further Re-escalation and weaning will be performed per initial protocol.

F. Pediatrician Follow-up:

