Risks include the possibility of unexpected toxicity from methadone. Methadone is a narcotic and as with all drugs in this class, respiratory depression may occur; however, it is less likely because the infants are already tolerant to opiates from *in-utero* exposure. The routine treatment for NAS infants at JHACH is oral morphine, a pure mu receptor opioid agonist. In comparison to morphine, methadone is in addition an N-methyl-d-aspartate agonist with a long half-life. Infants are routinely closely monitored during the initiation and escalation phases of treatment. Studies have failed to show any additional risk of respiratory depression of methadone as compared to oral morphine. In addition, the half-life of methadone makes it less likely for its cessation to result in acute symptomatology.

Other infrequent side effects may include rashes and feeding problems. Rashes from drugs are uncommon in babies. Feeding problems including uncoordinated sucking and swallowing are common in infants who are withdrawing from narcotics. The scoring system used to monitor the babies includes monitoring both excess sleeping with poor wake-alert feeding cycles and infant feeding ability scales to allow for appropriate adjustments of dosing thus minimizing these side effects.

b. Steps taken to minimize the risks:

The infants will be closely monitored for the following: heart rate, respiratory rate, temperature, oxygen saturation and blood pressure in the NICU during the initiation and escalation of methadone. All infants in the JHACH NICU have routine continuous oxygen saturation monitoring and also have continuous cardiorespiratory monitoring as standard of care. The usual medication for reversal of acute opioid overdose is naloxone. However with chronic opioid use this reversal is contradicted because it would precipitate acute narcotic withdrawal. Instead supportive care would include atropine if needed for bradycardia, intravenous fluids and vasopressor agents if needed for hypotension and ventilator support if needed for inadequate respiration.

All records are confidential. The data sheets are coded such that personal identifiers are omitted. Consent forms are in the infant's chart and copies are locked in the office of the PI.

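### Section 7.a presents excess sleeping and feeding ability as a basis for adjusting the dose, but no written methadone rule names them or lowers or withholds a dose for them, and expected, non-serious over-sedation is not captured as an adverse event

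*Combined protocol and SAP*

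**What the plan says.** Section 7.a lists rashes and feeding problems as other infrequent side effects, then offers a safeguard: "The scoring system used to monitor the babies includes monitoring both excess sleeping with poor wake-alert feeding cycles and infant feeding ability scales", with the stated purpose "to allow for appropriate adjustments of dosing thus minimizing these side effects".

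The dosing rules are under Study Procedures, in the Demonstration Study Methadone Protocol. Treatment starts on scores: "Initiate protocol for infants with 2 consecutive Finnegan scores > 8". "Starting dose is 0.1 mg/kg/dose Q 6 hours (Table 2 - Step 1"), with a minimum of 8 doses in Table 2. The first step down is "Initial weaning: wean after 48 hours of stable scores (i.e. 2 consecutive 24 hour Finnegan score averages < 8"). After that: "Subsequent weaning: Wean to the next step if the 24 hour Finnegan score average is < 8". A 24-hour average of 8-10 means no wean, and 11 or more means escalation.

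Discharge on methadone (part C) requires a dose of 0.04 mg/kg or less, "A history of successful weaning of methadone for a least 3 days prior to discharge, and" no re-escalation in the preceding 72 hours. The treating team must also judge the infant stable.

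The Adverse Events section restricts capture to three classes: events at least possibly related to the drug and also unexpected; serious events; and six listed events of interest. The listed events include a respiratory rate below 20/min and need for respiratory support. Sedation is not listed.

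**The concern.** A risk section tells the ethics board how a hazard is controlled. Here the stated control is a dose adjustment informed by sleeping and feeding, and a reader would expect to find that adjustment in the dosing rules. The step rules look in one direction: they respond to signs of withdrawal and have no branch for signs of too much drug.

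Two things are at stake. First, the protocol describes a safeguard that staff following its rules would not find, either in the NICU or during home treatment. Second, the independent safety monitor is asked to focus mainly on drug-related toxicity, yet the adverse-event filter can leave out a mild, foreseeable form of it.

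**Working it through.** **1. The plan's own timing figure.** Table 2, Step 1: 8 doses x 6 h = 48 h. This matches the 48 hours of low scores required before the first wean.

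**2. Every printed rule, with its trigger and action.**

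| Rule | Trigger | Action |
|---|---|---|
| Start | 2 consecutive scores > 8 | Step 1 |
| First wean | two 24-h averages < 8 | next step |
| Later weans (Tables 2, 3) | 24-h average < 8 | next step |
| No wean | 24-h average 8-10 | stay |
| Escalate | 24-h average >= 11 | back one step; Step 1A if Step 1 fails |
| Physician review | 2 consecutive scores showing severe withdrawal | re-escalate, extra dose, or earlier dose |
| Second drug (part G.1) | average >= 11 at maximal dosing | phenobarbital, off-treatment |
| Discharge (part C) | dose ceiling, 3 days of weaning, no re-escalation, team judgement | home on methadone |
| Stop (part D) | lowest step and average <= 6 | discontinue |
| Resume (part E) | rebound, scores > 8 on 2 assessments after comfort measures | last dose |
| Home re-escalation (part G.2) | 2 consecutive scores > 8 despite comfort measures | previous dose |
| Re-admit (part G.2) | repeated re-escalation without control, or reaching a set dose | hospital, off-treatment |

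Rules that name sleep, alertness or feeding: 0 of 12. Rules that lower or withhold a dose because of them: 0 of 12. All three options open to the reviewing physician give more drug or earlier drug.

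**3. Could the items act through the score?** Section 7.a says the scoring system includes them, but the score sheet is not in the document, so both cases are needed.
- *They add points.* A sleepy, poorly feeding infant scores higher and moves towards no wean (8-10) or escalation (11 or more). The Background section lists sleep disturbance and poor feeding among the signs of withdrawal, so a drug effect could be scored as withdrawal.
- *They sit outside the total.* No rule refers to them.

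In neither case does a written rule lower or withhold a dose because of these signs.

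**4. What a run of low scores does.** With every 24-hour average below 8, Table 2 gives:
- Step 1: 48 h, at 0.1 mg/kg x 4 doses a day = 0.4 mg/kg/day.
- Start of Step 4: 48 + 24 + 24 = 96 h, at 0.04 x 2 = 0.08 mg/kg/day.
- Reduction from Step 1 to Step 4: 1 - 0.08/0.4 = 80%.
- End of Step 8: 48 + 6 x 24 + 24 = 216 h, or 9 days.

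The dose therefore falls. The printed timetable is the same whatever the reason for the low scores.

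**5. What reaches the safety monitor.** Take an episode of excess sedation without respiratory signs.
- Serious (for example, it prolongs the stay): captured.
- Not serious, at least possibly related, and unexpected: captured.
- Not serious and expected: not captured, because it is not one of the six listed events.

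The plan defines expectedness by the package insert, which is not in the document. The gap therefore applies to sedation of a kind and severity that the insert lists. That the insert lists any is an assumption.

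**The case against.** The strongest reply has four parts.

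*The score may already contain these items.* If so, they do enter the rules indirectly. This stands as a limit on the wording: it cannot be said that sleep and feeding have no influence on dosing. It does not supply the safeguard, because added points move the infant away from a lower dose.

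*Section 7.a concerns feeding problems, not opioid excess in general.* This stands. Section 7.a treats respiratory depression separately and calls feeding difficulty common in withdrawal, and section 7.b gives vital-sign and cardiorespiratory monitoring and supportive care. The point is confined to the one safeguard that the sentence describes.

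*Other protection exists.* This also stands. Beyond NICU monitoring, the plan has twice-daily home nursing visits with general assessment, teleconferences every 3-4 hours, pediatrician visits, the treating team's judgement at discharge, and stopping boundaries for severe events and for moderate events needing oxygen, flow or tactile stimulation. None of these is linked to a dose step, but they are real.

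*Silence is not an instruction to dose.* Correct. Minimum dose counts set the pace of weaning, and nothing says that a dose must be given despite toxicity.

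A reader might infer something stronger: that an over-sedated infant would be declared stable, kept on full dosing and sent home unnoticed. The document does not support that. A low average triggers a wean, discharge needs a much lower dose and a clinical judgement, and such an infant's score cannot be known without the score sheet. The label of stable scores in Table 2 governs weaning. The discharge definition in part C is separate and has no score threshold of its own.

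**Conclusion.** The point holds as a mismatch between two parts of the protocol, together with a narrow recording gap. Section 7.a cites a dose adjustment that 0 of 12 printed rules contain, and this is so whether or not the items count towards the Finnegan total. Over-sedation that is both expected and non-serious falls outside all three capture classes.

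The conclusion covers the written rules only. It makes no claim about how staff would act, how often over-sedation would occur, or which dose would be right. It rests on the rules as printed and, for the recording gap, on the package insert listing sedation at the severity seen. It has no effect on the primary analysis or on any sample-size, power or alpha figure. It is worth correcting because it concerns infant safety during treatment that continues at home, and because correction is cheap.

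**What to change.** 1. Reconcile section 7.a with the Demonstration Study Methadone Protocol and parts C to G. The sponsor's clinicians decide how, or whether, the sleeping and feeding items bear on dosing. The dosing section should then say so, or section 7.a should stop presenting them as a basis for adjustment. State whether the items count towards the Finnegan total. No dose or clinical rule is proposed here.

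2. Add excess sedation, described by the sleeping and wake-to-feed pattern that section 7.a says is already monitored, to the adverse events of interest. The monitor then sees it whether or not it is expected or serious.

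The cost is protocol wording and one line on the adverse-event form. The downside is some non-specific reports, because feeding problems are also common in withdrawal. For that reason isolated feeding difficulty need not be listed.
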